7.7 Trial assessments

The study comprises a screening period of maximum 21 days, randomisation (d-21 to d-1), a baseline visit at day 0 (start of treatment), a treatment period of 24 weeks and a post-treatment period of 2 weeks (24-26 weeks). Considering the pragmatic nature of the proposed trial clinic visits are kept to an absolute minimum.

The **clinical visits** take place at day 0 (V1), week 4 (V2), 12 (V3), 18 (V4), 24 (V5) and 26 (V6) which is comparable to a schedule which would be maintained in routine clinical care. A deviation of +/- 5 days is allowed for the clinical visits. The assessments made at these visits are (*routine care assessments are indicated in bold):*

- Documentation of the study intervention: number of patches (lidocaine and capsaicin), location, dosage used (pregabalin and gabapentin), compliance and discontinuation check
- Documentation of size of painful area
- Assessment of adverse events
- Assessment of systemic drug related side effects (e.g. dizziness, fatigue, vertigo, somnolence, headache, blurred vision) (not on baseline visit)

- · Concomitant medication use
- Only during V2 and V4 clinical sensory testing will be repeated (using the Boston Bedside Quantitative Sensory Testing Battery)

The majority of the assessments (patient reported outcomes and experiences) will be performed by making use of an online platform, enabling patients to complete the different assessments themselves without having to schedule a clinic visit. The use of the online platform will significantly reduce the work load for the patients involved in this study. Per regular weekly online assessment, the required time investment will not exceed 15 minutes. The online assessments on a monthly basis (n = 7 in total) will never require more than 30 minutes (which can be split over different moments).

Online assessments: weekly basis

A deviation of max. 48 hours is allowed for the completion The following procedures and assessments will be carried out:

- Assessment of reduction in pain intensity using PI-NRS
- Assessment of analgesic medication use (using MQS III)
- Quality of sleep: Sleep NRS
- Assessment of systemic drug related side effects (not collected at baseline)
- Discontinuation of study drug (not collected at baseline)
- Participation in activities: Utrecht Work Engagement Scale-9

Online assessments: monthly basis (baseline, week 6, 10, 14, 18, 22)

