Vomiting	1 – 2 episodes (separated by 5 minutes) in 24 hours.	3 – 5 episodes (separated by 5 minutes) in 24 hours.	>=6 episodes (separated by 5 minutes) in 24 hours; tube feeding, TPN or hospitalization indicated.	Life- threatening consequences; urgent intervention indicated.	Death
Dizziness	Mild unsteadiness or sensation of movement.	Moderate unsteadiness or sensation of movement; limiting instrumental ADL.	Severe unsteadiness or sensation of movement; limiting self care ADL.	-	-
Depressed level of consciousness	Decreased level of alertness.	Sedation; slow response to stimuli; limiting instrumental ADL.	Difficult to arouse.	Life- threatening consequences.	Death.

If cross-over of active treatment (pregabalin to gabapentin, lidocaine to capsaicin or capsaicin to lidocaine) occurs as well as if active treatment is stopped, the corresponding visits will be performed as described in the flow chart. The patient remains in the study and will be followed up as if he/she was still on active treatment.

All withdrawals will be documented and the reason for withdrawal recorded in the patient file (medical record) and in the eCRF and discussed, as necessary, in the clinical trial report.

Patients who fail screening will not be included in the analysis but will be entered into the

trial database (eCRF – OpenClinica). The reason for failure will be documented in the patient file and in the eCRF and reported descriptively and by patient listing in the report of this trial.

Patients who fail screening will be replaced. Patients who initially may not meet eligibility criteria (e.g. for administrative reasons or assessments are out of time window) may be re-screened at investigator's discretion after consulting with the Sponsor (CI). Patients who withdraw from the study after randomisation will not be replaced.

The sponsor reserves the right to discontinue the trial overall or at a particular trial site at any time for the following reasons:

- Emergence of any efficacy/safety information that could significantly affect continuation of the trial;
- Violation of good clinical practice (GCP), the clinical trial protocol (CTP), or the contract by a trial site or investigator, disturbing the appropriate conduct of the trial.

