In Haanpää et al.³⁶ and Baron et al. patient completion rates for the follow-up of 90% and 96% respectively are reported which seems - bearing in mind that the burden on the patients in follow-up assessments is extremely low in the proposed pragmatic trial - realistic to us. However, in the systemic treatment arm drop-out from the study medication will be considerable (due to side effects). Indeed, in Baron et al. 39 of 153 patients (25.5%) of the pregabalin group discontinued the study medication and Haanpää et al. reports 41 out of 277 (14.8%) of the pregabalin arm withdrawing from the study medication. If we combine the two studies, we get 80 out of 430 or 18.6% drop out rate. For capsaicin 8% patch the withdrawal from study medication was 6 out of 282 (2.1%) and for lidocaine 5% plaster 9 out of 155 (5.8%) withdrew. Hence, we anticipated an average drop-out rate between 5.8% and 18.6% of 12% for each treatment arm which implies 197 patients per treatment group. In total, we would need to randomize **591 patients** in a 1:1:1 way to the 3 treatment arms.

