- The percentage of systemic drug-related side effects will be evaluated at 6 and 26 weeks using Chi-square test or Fisher's exact test. The evolution of the percentage of systemic drug-related side effects over time will be analyzed using a generalized linear mixed effects model using the clinical visit data and

the self-reported patient data.

- Discontinuation of study drug or study withdrawal: the percentage of study
 withdrawal will be compared after 6 and 26 weeks with a Chi-square test or
 Fisher's exact test whatever is appropriate based on assumptions. The time to
 discontinuation will also be studied in a time-to event analysis comparing the
 different treatment arms. The self-reported patient data will be used for this.
- Global perceived effect (GPE), effect on mood (Hospital Anxiety and Depression Scale), quality of sleep (Sleep-NRS and ISI), participation in activities (Utrecht Work Engagement Scale-9), impact of pain on functioning (interference – BPI), and Work Productivity and Activity Impairment (WPAI-Neuropathic Pain) will be compared at 26 weeks using linear regression and over time using linear mixed models.
- Similar to the primary outcome the treatment effect on the secondary outcomes will be estimated in a model with adjustment for confounders and including site as a random effect

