10.3.4 Procedure(s) to account for missing or spurious data

Most of the data is collected through the online platform. A deviation of max. 48 hours or 7 days will be allowed for the completion of the different assessments at every time point (weekly versus monthly).

 The proposed linear mixed model allows that subjects have missing values at certain time points as the model uses all available data points per subject. The missing value assumption of the model is Missing At Random which means that missing values can only be dependent on the observed responses which seems a reasonable assumption in this case.

The study coordinator follows up on the missing data and records any reasons for missing data in patient file (medical record) and the eCRF (OpenClinica).

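### Time to study-drug discontinuation rests on patient self-report alone, so stops recorded only by the site drop out of a tolerance endpoint

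*Protocol*

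**What the plan says.** Section 3.5 lists time to discontinuation of the study drug, and the proportion stopping it, among the secondary endpoints. They serve the drug-tolerance objective in section 3.2. Section 10.3.3 plans a time-to-event comparison of the arms and then states: "The self-reported patient data will be used for this". Section 7.7 shows what that source is: an item on stopping the study drug in the weekly online questionnaire.

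The protocol also collects stopping from the site side:

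- Section 7.7 includes a "compliance and discontinuation check" in the documentation made at clinic visits. Section 7.9 repeats it for week 26.
- Section 7.11 states: "All withdrawals will be documented and the reason for withdrawal recorded in the patient file (medical record) and in the eCRF".
- Section 8.7 sends all dose changes of the systemic drugs to the patient file and the eCRF.
- Section 8.8 sets up drug accountability and records each in-hospital capsaicin application in the eCRF.

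On follow-up after stopping, section 7.11 says: "The patient remains in the study and will be followed up as if he/she was still on active treatment". On gaps in the data, section 10.3.4 says: "The study coordinator follows up on the missing data and records any reasons for missing data in patient file (medical record) and the eCRF".

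For side effects, the bullet just before the discontinuation bullet plans a generalized linear mixed effects "model using the clinical visit data and" the patients' own reports. For discontinuation, only the patients' reports are named.

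**The concern.** With self-report as the only source, an event exists only if the patient fills in a form after stopping. Section 7.12 lists the ways in which participation ends early: withdrawal of consent, refusal of follow-up and loss to follow-up. Its own example of refusal is a patient who leaves because of adverse events and declines further contact. Such a patient is a likely drug stopper and sends no further report. The site may well know of the stop and have entered it with its reason, but the sentence in section 10.3.3 gives the analysis no way to use that entry.

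At stake are the absolute stopping rates and the absolute differences between systemic and topical treatment. These are the figures a reader would use to judge tolerance.

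**Working it through.** **Inputs from the protocol (section 10.1).** The protocol states no figure for the discontinuation analysis itself, but its stopping rates reproduce:

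- pregabalin: "we get 80 out of 430 or 18.6% drop out rate"; 80/430 = 18.6%
- lidocaine: 9/155 = 5.8%
- capsaicin: 6/282 = 2.1%
- patients per arm: 173/(1 − 0.12) = 196.6, rounded up to 197

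Expected stoppers per 197 are 36.7, 11.4 and 4.2.

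**Assumption.** A share f of stoppers never reports again. The documents give no value for f, so 10, 25 and 50% are shown.

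**Case 1: the same f in every arm.** Observed proportion = (1 − f)p. Missed events = 197·f·p.

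| f | Missed: pregabalin | Missed: lidocaine | Missed: capsaicin | Pregabalin − lidocaine | Pregabalin − capsaicin |
|---|---|---|---|---|---|
| 0 | 0 | 0 | 0 | 12.8 points | 16.5 points |
| 10% | 3.7 | 1.1 | 0.4 | 11.5 | 14.8 |
| 25% | 9.2 | 2.9 | 1.0 | 9.6 | 12.4 |
| 50% | 18.3 | 5.7 | 2.1 | 6.4 | 8.2 |

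Two-sided 5% power to compare the pregabalin and lidocaine proportions falls from 97.5% to 95.8, 91.3 and 75.8%.

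If silent stoppers are instead censored at the moment of stopping, the Kaplan-Meier incidence is 1 − (1 − p)^(1 − f). For pregabalin this gives 16.9, 14.3 and 9.8% against 18.6%.

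**Effect on the hazard ratio.** On the same model each arm's cumulative hazard, −ln(1 − p), is multiplied by (1 − f). The factor cancels in the ratio. Pregabalin against lidocaine stays at ln(1 − 0.186)/ln(1 − 0.0581) = 3.44, and pregabalin against capsaicin at 9.57.

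**Case 2: only pregabalin stoppers fall silent.** The hazard ratio against lidocaine becomes 3.44·(1 − f), which is 3.10, 2.58 and 1.72. Power for the difference in proportions falls to 93.2, 77.5 and 25.8%.

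**How large could f be?** Section 10.1 cites follow-up completion of 90% and 96%, so 4 to 10% do not complete: 8 to 20 of 197. If every pregabalin non-completer were a silent stopper, f would be 0.04/0.186 = 22% to 0.10/0.186 = 54%. This is a ceiling, not an estimate.

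**The case against.** The best defence is that weekly self-report is a reasonable choice for dating a stop. Clinic visits fall at weeks 4, 12, 18 and 24, with up to 8 weeks between them. Accountability depends on patients bringing their boxes, and section 8.7 lets patients stop by themselves at any time. The site record is therefore not a complete source either. This stands, and it is why the sources should be combined rather than one replaced by the other.

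The protocol also works against silence. Stoppers stay in follow-up (7.11), their data are collected as for adherers (10.3.2), the platform sends messages about missing entries (11.3.1), the coordinator chases gaps (10.3.4) and paper forms exist (7.7). A patient who skips some weeks and answers later can still report the stop, so only permanent silence matters. This lowers f but does not bring it to zero. What the coordinator learns goes to the patient file and eCRF, not into the self-report.

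It is also unclear whether the sentence on the source governs the whole bullet or only its time-to-event part. The same bullet separately compares percentages of study withdrawal, which would show some of the patients who leave.

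A reader might infer that the protocol censors such patients at their event. It states no censoring rule for this endpoint, and the statistical analysis plan may set one. The loss of the event follows from the named source whatever censoring date is chosen.

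**Conclusion.** The point holds as an avoidable under-count in one secondary tolerance endpoint. The source is stated, not left open, and it omits records that the protocol already collects. Absolute stopping rates and absolute differences are biased towards zero when f is equal across arms. At f of 10 to 50%, the pregabalin-lidocaine difference loses 1.3 to 6.4 of its 12.8 points. These figures rest on the protocol's stopping rates applying in this trial and on an assumed f.

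Two stronger readings are tempting and not supported. The first is that stopping is under-counted most where it is most frequent. With equal f this is true of the number of events, but not of the proportion lost. That proportion is the same in every arm for simple percentages. For Kaplan-Meier incidence it is slightly smaller on pregabalin: at f = 25%, 18.6 to 14.3% is a 23% loss, against 24% for lidocaine (5.81 to 4.39%). The second is that the comparison between arms is biased on the hazard-ratio scale. That needs silence to be more common in one arm, and the documents give no figure for it.

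**What to change.** Replace the sentence on the data source in section 10.3.3 with:

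> The date of permanent discontinuation is the earliest stop date recorded in any source (weekly self-report, visit discontinuation check, eCRF withdrawal record, drug accountability). An analysis using self-report alone is a sensitivity analysis.

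The word permanent is needed because section 7.11 lets patients resume treatment after an interruption.

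No new data are required, since section 11.1 already brings the medical-record and platform data together in the eCRF. The cost is some reconciliation where sources disagree, and coarser dates for stops known only from a visit. A patient lost to both forms and visits without any recorded stop remains unobserved, so the change reduces the under-count but does not remove it.

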10.3.4 Procedure(s) to account for missing or spurious data

Most of the data is collected through the online platform. A deviation of max. 48 hours or 7 days will be allowed for the completion of the different assessments at every time point (weekly versus monthly).

 The proposed linear mixed model allows that subjects have missing values at certain time points as the model uses all available data points per subject. The missing value assumption of the model is Missing At Random which means that missing values can only be dependent on the observed responses which seems a reasonable assumption in this case.

The study coordinator follows up on the missing data and records any reasons for missing data in patient file (medical record) and the eCRF (OpenClinica).

10.3.5 Other statistical considerations

An important exploratory goal of this study is to design a profile of the patient-selective sensory phenotypes suitable for both topical treatment options. We will use the 3 stratifying variables as specified in our stratified randomisation (hyperalgesia/allodynia, dysesthesia, duration of pain) and test for a significant interaction between the treatment and the stratifying factor to see if the treatment effect is modified by this factor.

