3.6 Exploratory endpoints

To design a profile of the patient-selective sensory phenotypes (using Neuropathic Pain Symptom Inventory (NPSI)) suitable for both topical treatment options. It is our special interest here to investigate the presence of mechanical allodynia in these patients and study the impact of the active treatment options on this sensory abnormality.

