4 TRIAL DESIGN

A multicenter three arm, 1:1:1 randomised, open-label comparative trial evaluating topical treatment options versus oral systemic treatment in adult patients suffering from localized neuropathic pain (LNP) syndromes. A wide variety of peripheral neuropathic pain syndromes will be included such as (but not limited to) post-herpetic neuralgia (PHN), post-surgical NP/post-traumatic NP/scar pain, post-amputation NP, post-radiation therapy NP, complex regional pain syndrome (CRPS) type 1.

591 adult patients suffering from LNP will be **randomised 1:1:1** to receive pregabalin, lidocaine 5% medicated plaster or capsaicin 8% patch. Stratification according to positive sensory phenomena such as hyperalgesia and allodynia, spontaneous positive sensory phenomena (such as dysesthesia) and duration of pain will be applied to keep the treatment arms balanced per stratum variable. The Neuropathic Pain Symptom Inventory (NPSI) will be used for this matter. Its factorial structure makes it suitable to capture different aspects of neuropathic pain (NP). The NPSI has been used in several doubleblind trials as a secondary outcome measure, with some dimensions being differentially sensitive to treatment effects.

Stratified randomisation by site and NPSI will be applied, and coordinated centrally which randomizes eligible patients to one of three treatment arms. All investigational medicinal products will be dispensed by the hospital pharmacies of the individual participating multidisciplinary pain centers as is now already routinely done. Relabelling is necessary by the hospital pharmacy since the lidocaine plasters are used off-label. All study drugs will need to be relabelled by the hospital pharmacies.

Patients who want to withdraw from the study medication will be offered an alternative according to standard clinical practice. This will imply that patients on the pregabalin arm will be offered an alternative systemic drug treatment (gabapentin) and patients on the topical arm will be offered a different topical drug (failing treatment with lidocaine medicated plasters will be treated with capsaicin patches and otherwise). Hence there will be no crossover from systemic to topical or vice versa, to preserve the comparison between the systemic versus topical treatment as much as possible during the trial.

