6.1 Inclusion criteria

Patients eligible for inclusion in this study must fulfil all of the following criteria:

- Subjects should be capable of giving their informed consent with sufficient knowledge of the Dutch, French or German language;
- Males and females, 18 years and older;
- Be assessed as suffering from moderate to severe neuropathic pain across the screening process with pain intensity (numeric rating scale – NRS) ≥ 4/10;
- At the time of screening pain symptoms have to be present for at least one (1) month, with a maximum of 24 months;
- Sensory disturbances present in the skin area of maximal pain;
- At the time of screening pain is clearly related to the presence of a localized neuropathic pain syndrome;
- Male or female patients of child producing potential* must agree to use contraception or take measures to avoid pregnancy during the study and until after the final treatment;
- Women can only be included after negative pregnancy test;

For female patients: Women of childbearing potential* must be willing and able to use an acceptable effective contraception until treatment discontinuation.

For male patients: Men who are fertile** with partners of childbearing potential must be willing to use an acceptable effective contraception until treatment discontinuation.

*A women is considered of childbearing potential (WOCBP), i.e. fertile, following menarche and until becoming post-menopausal unless permanently sterile. Permanent sterilisation methods include hysterectomy, bilateral salpingectomy and bilateral oophorectomy. A postmenopausal state is defined as no menses for 12 months without an alternative medical cause.

**A man is considered fertile after puberty unless permanently sterile by bilateral orchidectomy.

Birth control methods which may be considered effective when used consistently and correctly:

- Combined (estrogen and progestogen containing) hormonal contraception associated with inhibition of ovulation:
 - Oral
 - Intravaginal
 - Transdermal
- Progestogen-only hormonal contraception associated with inhibition of ovulation:
 - Oral

- Injectable
- Implantable
- Progestogen-only oral hormonal contraception, where inhibition of ovulation is not the primary mode of action
- Intrauterine device
- Intrauterine hormone-releasing system
- Male or female condom with or without spermicide
- Cap, diaphragm or sponge with spermicide
- Bilateral tubal occlusion
- Vasectomised partner
- Sexual abstinence

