7.3 The randomisation scheme

Randomisation will be performed at day -21 to day -1. Stratified randomisation will be used. Stratification according to site and the 3 stratifying variables: hyperalgesia/allodynia (absent or not), spontaneous positive sensory phenomena (such as dysesthesia) (absent or not) and duration of pain (less or more than 3 months) will be applied to keep the treatment arms balanced per stratum variable.

We will use a **minimisation procedure to randomize**. Minimisation assures similar distribution of selected participant factors between study groups. The first participant is truly randomly allocated; for each subsequent participant the imbalance score is computed based on all previous allocations as well as the hypothetical allocation of the current patient to each treatment. The preferred treatment is then selected by choosing the treatment allocation associated with the smallest imbalance score.

The distance measure used to calculate the imbalance score is marginal balance. Marginal balance computes the cumulative difference between every possible pairs of level counts (i.e. the number of patients in that particular factor level).

The allocation of the new patient is then made at random with a heavy weighting in favour

of the intervention that would minimise imbalance (a probability of 0.75 will be used). The remaining probability is equally divided between the non-preferred treatments.

Method of implementing the allocation sequence

A web based randomisation system QMinim will be used.

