7.6 Baseline data (pre-randomisation, to be collected before randomisation)

The baseline data will be collected between one week before day 0 and at least 48 hours before day 0 through the online system. Baseline data will be collected in all cases before the patient is randomised and starts the treatment. The researcher will be able to check the completion of the baseline data in the online system.

Baseline status (V1) on the following variables (*measurements belonging to standard care are indicated in bold*):

- Health-related quality of life (EQ-5D-5L)
- Medication use (MQS III Medication Quantification Score)
- Pain using PI-NRS (pain intensity) and NPSI (Neuropathic Pain Symptom Inventory)
- The Pain Intensity Numeric Rating Scale (PI-NRS) is an 11-point scale for patient self-reporting of pain
- The Neuropathic Pain Symptom Inventory (NPSI) is a 12-item patient reported outcome measure that contains 10 descriptors representing 5 dimensions of pain (burning pain, deep/pressing pain, paroxysmal pain, evoked pain and paresthesia/dysesthesia) and 2 temporal items designed to assess pain duration and the number of pain paroxysms
- Quality of life of the patient using several questionnaires: Insomnia Severity Index (ISI), quality of sleep (NRS), HADS (Hospital Anxiety and Depression Scale)
- The Insomnia Severity Index (ISI) is a validated seven-item patient questionnaire used to quantify insomnia severity
- The Hospital Anxiety and Depression Scale (HADS) is a self-rated questionnaire to detect states of depression, anxiety and emotional distress
- Functional status of the patient using several questionnaires: Interference BPI (impact of pain on functioning), Utrecht Work Engagement Scale-9 and WPAI (Work Productivity and Activity Impairment)

Demographics will be collected at the time of the screening where the following variables are considered important (all belonging to standard clinical care): age, gender, level of education and family situation.

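### Treatment-by-phenotype interactions are specified only on three two-level randomisation factors, although NPSI dimension scores and pain duration could be used as continuous modifiers

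*Protocol*

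**What the plan says.** Section 3.6 sets the exploratory aim: "To design a profile of the patient-selective sensory phenotypes (using Neuropathic Pain Symptom Inventory (NPSI", with a special interest in whether mechanical allodynia is present. Section 10.3.5 calls the goal important and fixes how it is analysed: "We will use the 3 stratifying variables as specified in our stratified randomisation (hyperalgesia/allodynia, dysesthesia, duration of pain) and test for a significant interaction". In full, the plan is to "test for a significant interaction between the treatment and the stratifying factor to see if the treatment effect is modified by this factor".

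Section 7.3 gives the form of those variables: "hyperalgesia/allodynia (absent or not), spontaneous positive sensory phenomena (such as dysesthesia) (absent or not) and duration of pain (less or more than 3 months". All three are two-level.

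Finer measurements exist. On the stratification by sensory phenomena, Section 4 says "The Neuropathic Pain Symptom Inventory (NPSI) will be used for this matter", and it justifies the instrument by its factorial structure and by the differing sensitivity of its dimensions to treatment. Section 7.6 describes the NPSI as a "12-item patient reported outcome measure that contains 10 descriptors representing 5 dimensions of pain", completed before randomisation. On duration, Section 6.1 states: "At the time of screening pain symptoms have to be present for at least one (1) month, with a maximum of 24 months".

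Section 2 also announces a stratified analysis on bedside sensory testing (QST) and NPSI symptoms, and a classification into irritable and non-irritable nociceptors. That class is two-level too, and no interaction test is described for it.

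**The concern.** A two-level factor is reasonable for balancing arms by minimisation. It does not follow that the test of effect modification should use the same cuts. If the treatment difference changes gradually with duration or with the severity of a sensory dimension, a test on a cut version has less power than a test on the score itself.

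The trial is sized for main effects, so interaction tests start out weak. A real gradient is then more likely to be reported as no interaction. Duration is the clearest case: it is a quantity with a 24-fold range, and Section 2 says short duration has positive predictive value for capsaicin. For the NPSI, the protocol's own reason for choosing it is dimensional. Yet the burning, deep/pressing and paroxysmal dimensions have no named interaction test, and the sensory information enters only as two flags.

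**Working it through.** **The plan's own figure.** Section 10.1 gives a difference of 0.08, SD 0.240, alpha 0.05/2 and power 80%. By normal approximation, n = 2 × (2.241 + 0.842)² × (0.240/0.08)² = 18 × 9.505 = 171.1, so 172 per arm. The t-test version gives 172.35, so 173. With 12% dropout, 173/0.88 = 196.6, so 197 per arm and 3 × 197 = 591. The plan's sample size reproduces and is not in question. The protocol states no figure for the interaction tests.

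**Information kept by a cut.** If modification is linear in a modifier X, the efficiency of testing a two-level version instead of X is the squared correlation between the two.

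- Normal score cut at proportion p: efficiency = φ(z_p)² / [p(1−p)].

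| Split | Kept | Lost |
|---|---|---|
| 50/50 | 0.637 | 36% |
| 30/70 | 0.576 | 42% |
| 20/80 | 0.490 | 51% |
| 10/90 | 0.342 | 66% |

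- Duration cut at 3 months. The protocol gives no distribution, so several are assumed over 1 to 24 months. For a uniform variable, efficiency = 3p(1−p). Uniform in months: p = 2/23 = 0.087, efficiency 0.238. Uniform in log months: p = ln 3/ln 24 = 0.346, efficiency 0.68. The other entries are from simulation.

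| Assumed distribution | Lost, effect linear in months | Lost, effect linear in log months |
|---|---|---|
| Uniform | 76% | 51% |
| Log-uniform | 59% | 32% |
| Truncated exponential (mean scale 4 to 15 months before truncation) | 59–72% | 33–45% |

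- Symptom flags. The protocol states neither the NPSI cut that defines absence, nor the prevalence, nor the item response range. Assume scores of 0 for absent and 1 to 10 for present, with 10% to 70% absent and three shapes among those affected. The flag then keeps between 0.268 and 0.916 of the information, a loss of 73% down to 8%. If presence itself is the modifier, nothing is lost.

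**Power for one pairwise interaction.** Inputs: SD 0.24 and 173 per arm from Section 10.1. Assumptions: EQ-5D as outcome, two-sided alpha 0.05, and a treatment difference that changes by b per SD of the modifier. SE of the slope difference = 0.24 × √(2/173) = 0.0258. Power = Φ(b/SE × √efficiency − 1.96).

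For b = 0.06, b/SE = 2.325:

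- continuous: Φ(2.325 − 1.96) = 64%
- normal score, median split: Φ(2.325 × 0.798 − 1.96) = 46%
- duration uniform, linear in months: Φ(2.325 × 0.488 − 1.96) = 20%
- duration log-uniform, linear in log months: Φ(2.325 × 0.824 − 1.96) = 48%

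For b = 0.04, b/SE = 1.550: 34% continuous, 24% with a median split, and 11% to 25% with the same two duration cases. For scale, b = 0.08 per SD would equal the trial's whole target effect, so slopes at the upper end are large.

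**The case against.** The strongest reply is that this is an exploratory aim with no power claimed, and that the functional form of a modifier is usually left to the analysis plan. The first half stands and limits the weight of the point. The second does not, because Section 10.3.5 commits to the stratifying variables in their randomisation form.

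A second reply is that a binary test may be the right one. Section 3.6 asks about the presence of allodynia, and Section 2 reasons partly in classes (irritable or not). This stands for the symptom flags and is a good reason to keep those tests. It does not cover duration, where nothing in the protocol argues for a step at 3 months.

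A reader might also infer more than the documents support:

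- That a third or more of the information is lost in all three tests. This needs a roughly linear effect. It holds for a normal score and approximately for duration, but not necessarily for absent/present symptoms.
- That the absent groups must be small because entry requires sensory disturbances. Section 6.1 does not require positive ones, the Appendix 5 screening tool accepts a negative or a positive sign, and the definition in Section 6 joins signs and spontaneous symptoms by and/or. No prevalence is given.
- That phenotype is examined nowhere else. Section 2 announces the stratified QST/NPSI analysis.
- That the eCRF holds only the duration category. Section 7.3 lists what the randomisation request contains, and Section 7.1.2 separately records relevant history. Neither names duration in months, and neither excludes it.
- That a fixed power gain is guaranteed. The gain depends on slope and distribution. With a loss of only 8%, it would be a few points.

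**Conclusion.** The point holds in limited form. The only interaction tests specified use two-level modifiers, while finer baseline NPSI data are collected and duration spans a wide range. The likely cost is greatest and best supported for duration: about 32% to 76% of the information under the distributions tried, if modification is roughly linear in months or log months. For a normally distributed score the loss is at least 36%. For the two symptom flags it cannot be fixed from the protocol and may be anything from none to about 70%.

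The power figures (64% against 46%, or 20% to 48% for duration) rest on an assumed slope of 0.06 per SD, an unadjusted 0.05 level and a single pairwise comparison. They illustrate the size of the loss and do not predict what the trial will find. This is a cheap improvement to an exploratory analysis. The sample size and the primary analysis are untouched.

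**What to change.** In Section 10.3.5, keep the three binary-factor interactions and add exploratory interactions of treatment with the continuous baseline NPSI dimension scores (evoked pain and paresthesia/dysesthesia) and with log pain duration. Check linearity, for example with a quadratic or spline term. Report all of them as exploratory estimates with confidence intervals. Confirm that duration in months is captured in the eCRF, and add the field if it is not.

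The cost is wording and possibly one field. The NPSI is already completed at baseline, and duration must already be established to check the 1 to 24 month criterion. The downside is more exploratory contrasts: two scores plus log duration over the three pairwise comparisons of Section 3.1 gives 3 × 3 = 9, beside the 9 from the binary factors, plus the linearity checks.
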